It has been recommended by subspecialty societies, including the American Association for the Study of Liver Disease (AASLD), that changes in liver fat content as quantified by magnetic resonance spectroscopy (MRS) or MRI proton density fat fraction (MRI-PDFF), can serve as an appropriate and clinically relevant primary outcome in early, phase 1 and 2 clinical trials of novel NAFLD therapeutics. Specifically, recent advances in MR-based imaging techniques now permit very accurate and validated means of quantifying intrahepatic lipids, via MRS and MRI-PDFF. Results of intrahepatic lipids (%) by MRS correlate closely with biochemical and histological assessment of liver triglyceride content, with an area under the receiver operating characteristic curve that exceeds 90%. Moreover, MRS measures global hepatic fat content across the entire liver (rather than from a small sample, from a liver biopsy), which is relevant as lipid content may be heterogeneous and thus liver biopsy could result in sampling error. Collectively, this robust prior evidence demonstrates that MRS (and MRI-PDFF) are robust and accurate means of quantifying steatosis for the primary endpoint assessment, in early-phase NAFLD interventional trials. In addition to these established MRI endpoints, the present study also includes an optional enrollment and month 6 liver biopsy, as part of the optional biopsy sub-study, but liver biopsy is not required for the main study.

II. SPECIFIC OBJECTIVES & ENDPOINTS

We will conduct a randomized, placebo-controlled trial to assess the feasibility and efficacy of aspirin for reducing liver fat, inflammation and fibrosis, in 80 adults aged 18-65 with established nonalcoholic fatty liver disease (NAFLD), confirmed by validated imaging modalities or by a clinical liver biopsy within 12 months of the screening visit.

Primary Efficacy Endpoint: 6-month absolute difference in % hepatic fat fraction (HFF), measured by 1H-MRS.

Key Secondary Endpoints:

1. Relative 6-month percentage change in HFF %, by 1H-MRS.
2. Proportion of patients with 30 percentage point or greater relative reduction in HFF, by 1H-MRS.
3. Absolute change in liver fat %, as measured by MRI-PDFF.
4. Relative percentage change in liver fat %, as measured by MRI-PDFF.

Non-Key Secondary Endpoints:

5. 6-month change in alanine aminotransferase (ALT) and aspartate aminotransferase (AST).

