11. Recruitment through a list of research subjects who have previously been recruited by our study team and have agreed to recontact for future studies.
12. Recruitment through materials distributed to providers who care for NAFLD patients outside of the Partners System.
13. Recruitment through the Research Match (Vanderbilt Recruitment Tool)

Subjects who express interest will be pre-screened via a REDCap questionnaire or phone.

IV. SUBJECT RECRUITMENT

A. Trial Population

Subjects responding to the initial recruitment advertisements will undergo initial screening and if deemed potentially eligible for participation, they will be contacted by telephone and invited to participate in a screening visit. Based on a conservative assumption of 60% rate of either screening failure or subjects declining to participate in a research study, we expect to screen 200 adult subjects and enroll a total of 80 subjects with confirmed NAFLD without cirrhosis.

B. Consent

All subjects will receive the consent form for the study as well as the Human Subject's Bill of Rights. These documents will be read by the study subjects and also reviewed carefully by the study subject with a clinician on the research staff, prior to participating in the study. Any questions, concerns, or ambiguities will be appropriately clarified by the study clinician prior to the patient signing consent. Potential study subjects will sign informed consent and only then will they begin participation in the study. If new information is ascertained during the study, we will modify our consent and re-consent our patients accordingly.

C. Randomization

After baseline testing, 80 subjects who meet all eligibility criteria will be randomized to one of two treatments for 6 months: 1) low-dose aspirin (81mg per day), or 2) identical, blinded placebo pills.

Study Endpoints	Month 0	Month 6
Intrahepatic Lipids (1H-MRS)	✓	✓
Inflammation / Fibrosis (LiverMultiScan, Fibroscan)	✓	✓
Specialized Proresolving Mediators (SPMs)	✓	✓
Untargeted Eicosanoids, Inflammatory Markers	✓	✓
PNPLA3 rs738409 genotype	✓	

*All subjects will have NAFLD with fibrosis stage 0-3 (F0-3) confirmed by prior clinical liver biopsy or by validated imaging modality.

V. STUDY PROCEDURES:

A. Overview of Study Design.

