 - NAFLD Fibrosis Score will be calculated from standard labs and subject characteristics (age, BMI, blood glucose, platelet count and albumin).
 - Serum and Plasma will be collected for future measurement of lipids, bile acids, other metabolites including adipokines and inflammatory markers.
- Additional peripheral blood (serum, plasma, and whole blood) from which we will extract DNA and RNA. This will permit testing (among other things) for the *PNPLA3* rs738409 genotype, as this is an established NAFLD risk locus, and testing of *PNPLA3* is currently recommended in NAFLD/NASH clinical trials⁸.
- Stool samples that have been collected at home will be brought with the patient on the Baseline Visit. A collection kit provided during the Screening Visit will allow minimal contact with the stool and allow easy storage of the sample until the day of the Baseline Visit. If the patient forgets or is unable to complete the sample collection prior to their appointment, they may be given the materials to mail their sample to the study staff.
- MRI: 1H-MRS of the right and left hepatic lobe will be performed to quantify hepatic lipid content and other fat depots. LiverMultiscan sequences will also be performed for noninvasive analysis of hepatic inflammation and fibrosis. During the same MRI session,

MRI-PDFF will also be performed. MRI will be repeated at the 6-month visit (for a total of 2 MRI sessions per subject).

- Fibroscan to measure liver stiffness via transient elastography (ultrasound). Fibroscan will be repeated at the 6-month visit (for a total of 2 Fibroscans per subject).
- Standard bionutrition assessment by trained research nutritionist.
- Assessment of adherence (month 6 visit) by returned pill count and by self-report.
- Three validated questionnaires will be administered to subjects:
 - The Paffenbarger Physical Activity questionnaire
 - The SF-36 health survey questionnaire
 - The semi-quantitative Food Frequency Questionnaire (FFQ)

Total Blood Drawn: Total blood volume from the participant is below 200ml for this Baseline Visit and for the Month 6 visit. As this is below 300ml over at least 6 hours, this does not result in added risk. Normal blood donation volume is 450-500ml.

2. Follow-up 3-month visit: (n=80)

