To address potential confounding due to meaningful weight loss between baseline and month 6, we will exclude any participant who loses $\geq 3\%$ body weight during the 6-month study period. We will construct separate, multivariable-adjusted regression models accounting for *a priori* defined clinical confounders, including age, sex, race/ethnicity, type 2 diabetes status at baseline, fasting insulin level at baseline, body weight and visceral adipose tissue (VAT) volume, as previously recommended for NAFLD clinical trials⁸. We will also repeat the analyses with missing data for primary and key secondary endpoints considered as nonresponses, by carrying forward the baseline values. We will also conduct subgroup analyses for the endpoints of

absolute change in HFF by MRS (primary endpoint) and relative HFF change by MRS (key secondary endpoint) in participants with significant, stage 2-3 fibrosis at baseline.

Sample Size, Statistical Power & Multiplicity Testing:

We anticipate a conservative drop-out rate of approximately 15%, thus we estimate an effective sample size of 68 patients. Based on prior studies of a dietary intervention for hepatic steatosis (Ryan et al.³⁹), and data from a meta-analysis of oral omega-3 supplementation and hepatic steatosis (Parker et al.⁴⁰) we expect an effect size of 3% with the standard deviation of the change in liver fat of 2.45, by ¹H-MRS. Applying these estimates, the probability is >90% that the study will detect a treatment difference at a two-sided 0.05 significance level⁴¹. The Holm procedure to control for multiple testing will be applied to the 4 key secondary outcomes, as follows: P=0.0125 for relative change in HFF by MRS, P=0.0167 for proportion achieving ≥30 percentage point reduction in HFF by MRS, P=0.025 for absolute change in HFF by MRI-PDFF, and P=0.05 for relative change in hepatic fat by MRI-PDFF. For the other non-key secondary outcomes no multiplicity adjustments will be employed. For exploratory outcomes, no multiplicity adjustments will be used.

Definitions of Analysis Sets:

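### The stage 2-3 fibrosis subgroup is analysed on its own, with no interaction term, no stage 0-1 estimate and no named staging rule, so it cannot show whether the effect differs by fibrosis

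*Combined protocol and SAP*

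**What the plan says.** Section VI.C (Data Analysis Plan) specifies ANCOVA for continuous outcomes, with treatment group as a fixed effect and the baseline value of the outcome as covariate. Among the subgroup and sensitivity analyses it lists absolute HFF change by MRS (the primary endpoint) and relative HFF change by MRS (a key secondary endpoint) "in participants with significant, stage 2-3 fibrosis at baseline". No treatment-by-fibrosis term, stage 0-1 analysis, stratification by fibrosis or expected subgroup size is given.

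On how stage is known:

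- Section I.A states that "liver biopsy is not required for the main study". Section V.A has slides from earlier clinical biopsies requested and read centrally where they exist.
- A note under section IV.C says that all participants have F0-3 disease confirmed by earlier biopsy or validated imaging. Section III.A lists such imaging (CT, 1H-MRS, MRI-PDFF, ultrasound) for confirming steatosis; elastography is not on that list.
- Section V.A plans, at baseline for every participant, "Fibroscan to measure liver stiffness via transient elastography (ultrasound" as well as LiverMultiScan and the NAFLD fibrosis score. Section V.C gives stiffness in kPa without a stage cut-off, and ties the high cut-off of the fibrosis score to F3-F4, not to stage 2-3.

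The sample size paragraph states: "we expect an effect size of 3% with the standard deviation of the change in liver fat of 2.45", and "the probability is >90% that the study will detect a treatment difference" "at a two-sided 0.05 significance level". It allows for a "conservative drop-out rate of approximately 15%, thus we estimate an effective sample size of 68 patients".

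**The concern.** A p-value from one stratum answers whether an effect is detectable there. It does not answer whether the effect there differs from the effect elsewhere. For that, the two stratum effects have to be compared, and the plan makes no comparison. If the subgroup result is not significant, nothing in the planned output separates a weaker drug effect in more advanced disease from a small sample. A reader could conclude that aspirin does not reduce liver fat in stage 2-3 disease when the effect is the same in everyone.

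The undefined group adds to this. F0-3 is the eligibility range, so confirming it does not separate stage 2-3 from stage 0-1. Histology, stiffness, LiverMultiScan output and the fibrosis score would not put the same people in the group, and the plan does not choose among them.

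**Working it through.** **Inputs.** From section VI.C: effect 3 points, SD of change 2.45, two-sided alpha 0.05, 80 randomised, 15% drop-out. From section IV.C: "80 subjects who meet all eligibility criteria will be randomized to one of two treatments for 6 months"; the ratio is not stated. Assumptions of mine: 1:1 allocation, equal SD in both strata, the same true effect in both strata, and a stage 2-3 share of 20%, 30% or 40%.

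**The plan's own figure.** 80 × (1 − 0.15) = 68, or 34 per arm. SE of the overall effect = 2.45 × √(2/34) = 0.594. The ratio 3/0.594 = 5.05 gives power of 99.9% (noncentral t, 66 df). The stated figure of more than 90% is reproduced.

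**Power inside the subgroup.** With n per arm, SE = 2.45 × √(2/n). Power comes from the noncentral t with 2n − 2 df and noncentrality 3/SE. The shares correspond to 68 × 0.20/2 ≈ 7, 68 × 0.30/2 ≈ 10 and 68 × 0.40/2 ≈ 14 per arm, leaving m = 34 − n per arm in stage 0-1.

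| Share | n / m per arm | SE in subgroup | 3/SE | Power in subgroup | Effect missed | Power in stage 0-1 |
|---|---|---|---|---|---|---|
| 20% | 7 / 27 | 1.31 | 2.29 | 56% | 44% | 99.3% |
| 30% | 10 / 24 | 1.10 | 2.74 | 74% | 26% | 98.6% |
| 40% | 14 / 20 | 0.93 | 3.24 | 88% | 12% | 96.5% |

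**Disagreement between strata under one common effect.** Let a be power in the subgroup and b power in its complement. P(disagree) = a(1 − b) + b(1 − a).

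- 20%: 0.558 × 0.007 + 0.993 × 0.442 = 0.004 + 0.439 = 44%
- 30%: 0.736 × 0.014 + 0.986 × 0.264 = 0.010 + 0.261 = 27%
- 40%: 0.877 × 0.035 + 0.965 × 0.123 = 0.031 + 0.119 = 15%

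The first term is the case in which only stage 2-3 is significant. It is 0.4%, 1.0% and 3.1%. Most of the disagreement comes from the smaller subgroup missing the effect.

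**What an interaction test would give.** SE = 2.45 × √(2/n + 2/m).

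| Share | SE of interaction | 95% CI half-width (1.96 × SE) | Difference detectable with 80% power (2.80 × SE) |
|---|---|---|---|
| 20% | 1.47 | 2.9 | 4.1 |
| 30% | 1.30 | 2.6 | 3.65 |
| 40% | 1.21 | 2.4 | 3.4 |

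At a 30% share, power for a 1.5-point interaction is 21%.

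**Effect of baseline adjustment.** The figures above are for unadjusted comparisons; the plan uses ANCOVA. If baseline HFF explained 25% of the variance of change (an assumption), the residual SD would be 2.45 × √0.75 = 2.12 and the miss rates would fall to about 32%, 15% and 5%.

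**The case against.** The strongest reply is that the plan claims nothing about effect modification. The analysis is listed with the subgroup and sensitivity analyses, outside the primary test and the Holm procedure, and no decision depends on it. It estimates the effect in a clinically defined group, and the fault would lie with a reader who over-interprets it. That limits the seriousness but does not remove the gap: the plan reports the stratum without the comparison needed to interpret it, and does not label it exploratory.

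A second reply is that an interaction test would be too weak to settle the question. This is correct. Its value is that the confidence interval shows the imprecision, which a lone subgroup p-value hides.

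A third is that the analysis plan is to be finalised before database lock in a double-blind trial, so the group can still be defined before results are known. This also stands; it means that the gap can be closed, not that it has been. The log of changes to the analysis plan after trial initiation records none.

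Finally, baseline adjustment would lower the miss rates, as the last step of the working shows.

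Three stronger readings are tempting but not supported:

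- **That most participants have no fibrosis stage.** The share with a biopsy is not stated, section IV.C says F0-3 is confirmed in all, and section V.A plans elastography for everyone. What is missing is the rule that turns these data into stage 2-3.
- **That a common effect would often appear only in stage 2-3.** At the planned 3 points this happens in 0.4% to 3.1% of trials.
- **That the strata would disagree about half the time or more.** Rates of 48% to 64% arise if the common effect is 2 points, but the plan assumes 3. The stage 0-1 test in that comparison is also one that the plan does not schedule.

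**Conclusion.** The point stands as a gap in a secondary analysis. As written, the stage 2-3 analysis cannot show, or rule out, a different effect by fibrosis, and its membership rule is not named. With the plan's own effect and SD, a common effect would be missed in the subgroup about 44%, 26% or 12% of the time, and the subgroup and its complement would disagree about 44%, 27% or 15% of the time. These figures rest on an assumed share of 20% to 40%, 1:1 allocation, equal SDs, 68 evaluable participants and no gain from baseline adjustment. The absence of the comparison rests on none of these assumptions. The primary analysis and its error control are untouched.

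**What to change.** Replace the stand-alone subgroup analysis with one ANCOVA per endpoint in all randomised participants, containing treatment, baseline HFF, baseline fibrosis group (stage 0-1 or 2-3) and treatment by fibrosis group. Report the treatment effect in each stratum and the interaction, all with 95% confidence intervals, labelled exploratory.

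Before unblinding, name the staging source and cut-off, the order of precedence where biopsy and non-invasive measures both exist, and the handling of anyone who cannot be classified. If the data have already been unblinded, report the definition as post hoc.

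A model with continuous baseline Fibroscan stiffness and its interaction with treatment can be added as optional support. It uses a measure planned for everyone and needs no cut-off, but it replaces stage with a surrogate and assumes a functional form, so it should not displace the two-stratum report.

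The cost is a few sentences of analysis plan text and no new data. The drawback, to be stated in the plan, is imprecision: the interaction SE is about 1.2 to 1.5 points, and at a 30% share a difference of about 3.65 points, larger than the planned main effect, is needed for 80% power. A non-significant interaction therefore cannot be read as showing equal effects.

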To ensure data entry accuracy, peer review of source documentation and case report forms in REDCap will be completed following MGB Study Data Management and Quality Assurance Plan Guidelines. Research coordinators will exchange subject files and review informed consents, case report forms, and adverse event logs for accuracy and completeness. Additionally, eCRFs in REDCap will be reviewed for accuracy and completeness using source data verification.

C. Statistical Analysis and Power

Data Analysis Plan:

This statistical analysis plan will be finalized before database lock. Baseline data between groups will be compared using chi-squared test or Fisher's exact test for categorical variables, and using ANOVA for continuous variables, with any non-normally distributed data log-transformed prior to analysis. If significant baseline group imbalance is detected on any particular variable, that variable will be included as a covariate in the analyses.

Absolute and relative changes in continuous outcomes between treatment groups will be calculated using analysis of covariance (ANCOVA), with treatment group at randomization included as a fixed effect, and the baseline value of the relevant outcome included as a covariate. Logistic regression will be used for binary outcomes (i.e., achievement of $\geq 30\%$ relative HFF reduction). For the primary analysis, all study endpoints will be analyzed using an intention-to-treat approach, using data from all randomly assigned participants in the full analysis set. The primary analysis will assume that missing data were missing at random³⁸, and data augmentation for missing observations will be conducted via multiple imputation, using all available non-missing data of the outcome measurement from the same treatment arm.

We will also utilize data from all participants who adhere to therapy as assigned and complete the final, 6-month visit for study outcomes (i.e., the per protocol analysis set).

We will conduct the following subgroup and sensitivity analyses for the primary and key secondary endpoints:

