41. Schoenfeld D. Statistical considerations for pilot studies. *International journal of radiation oncology, biology, physics* 1980;6:371-4.

Changes to Study Protocol After Trial Initiation Date:

- Version 4 (Amendment 2; approval date: 09/10/2019) updated the informed consent process descriptions.
- Version 5 (Amendment 5; approval date 10/02/2019) increased the upper age limit from 65 to 70 years; changed the frequency of follow-up phone calls from twice monthly to once monthly as recommended by the MGB QI team; and updated the funding information.
- Version 6 (Amendment 8; approval date 01/06/2020) updated the format of the SF-36 questionnaire; changed the compensation scheme for subjects, while keeping the total compensation for the overall trial unchanged; included the option of a serum pregnancy test for women of childbearing potential (in addition to urine pregnancy test); and included updated written instructions for stool collection kits, for subjects.
- Version 7 (Amendment 10; approval date 09/30/2020): added an oral microbiome sample to the baseline and month 6 time points; updated the payment distribution scheme for each study visit.
- Version 8 (Amendment 11; approval date 11/12/2020): clarified the exclusion criteria for thrombocytopenia by including the definition of lower platelet count threshold of 100K/uL.
- Version 9 (Amendment 12; approval date 02/19/2021): added an optional pre-treatment and/or post-treatment liver biopsy.
- Version 10 (Amendment 17; approval date 08/05/2022): added institution-wide research announcements as an additional method of potential recruitment.

Changes to Statistical Analysis Plan After Trial Initiation Date: none

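### The plan names Holm for the four key secondary endpoints but fixes Holm's step levels to named endpoints, so the printed rule contradicts the method

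*Combined protocol and SAP*

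**What the plan says.** Section VI.C, under Sample Size, Statistical Power & Multiplicity Testing, reads: "The Holm procedure to control for multiple testing will be applied to the 4 key secondary outcomes, as follows: P=0.0125". It attaches that first level to the relative change in hepatic fat fraction (HFF) by MRS. It then gives 0.0167 to the responder proportion by MRS and 0.025 to the absolute change by MRI-PDFF, and ends "and P=0.05 for relative change in hepatic fat by MRI-PDFF".

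This is the order in which Section II lists the key secondary endpoints. The second item there is "Proportion of patients with 30 percentage point or greater relative reduction in HFF, by 1H-MRS".

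Neither section says that the p-values are ordered, or that testing stops after a failure. The Data Analysis Plan in VI.C says "This statistical analysis plan will be finalized before database lock", but the document closes with "Changes to Statistical Analysis Plan After Trial Initiation Date: none", so no later text settles the point.

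**The concern.** Holm's levels belong to ranks, and ranks are known only once the p-values are. A list that fixes each level to an endpoint in advance is a different rule. A programmer following the sentence would test the relative MRS change at 0.0125 even if it had the largest of the four p-values, where Holm would test it at 0.05.

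The sentence can be read in three ways:

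1. The name governs and the list is shorthand for the step levels. This is Holm.
2. The list is a gated sequence in the printed order, stopping at the first failure. This controls error but is not Holm.
3. The list is literal: four free-standing levels with no stop. This does not hold error at 5%.

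The same data can support different key secondary claims under each reading. Because the plan does not choose, the choice could be made after the results are known.

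**Working it through.** **Reproducing the printed levels.** For four endpoints and a family level of 0.05, Holm's steps are 0.05/4 = 0.0125, 0.05/3 = 0.0167, 0.05/2 = 0.025 and 0.05/1 = 0.05. All four printed figures match. The numbers are right; their assignment is what is wrong.

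**Error of the literal list, all four nulls true.**

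- Upper bound: 0.0125 + 0.0167 + 0.025 + 0.05 = 0.1042.
- Independent tests: 1 − (0.9875 × 0.9833 × 0.975 × 0.95) = 0.1006.
- Correlated tests: the documents give no correlations, so a common correlation ρ is assumed, with normal test statistics and two-sided tests. The literal-list values at ρ from 0.5 come from numerical integration; the Holm values are simulated.

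| ρ | Literal list | Ranked Holm |
|---|---|---|
| 0 | 10.1% | 4.9% |
| 0.5 | 8.8% | 4.3% |
| 0.7 | 7.6% | 3.7% |
| 0.8 | 6.8% | 3.2% |
| 0.9 | 5.9% | 2.6% |
| 0.95 | 5.4% | not needed |

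The gated sequence gives 1.25% at every ρ when all nulls are true, because nothing is tested unless the first endpoint passes at 0.0125.

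All four endpoints measure liver fat, so ρ from 0.7 to 0.95 is the plausible range. If the responder endpoint is less correlated with the others (0.5 to 0.7) than the continuous endpoints are among themselves (0.8 to 0.95), the literal list gives 6.2% to 7.5%.

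**Some endpoints truly affected.** With independent tests and very large effects on the first one, two or three listed endpoints, the literal list gives 8.9%, 7.4% and 5.0%. Holm gives 4.9%, 4.9% and 5.0%. The gated sequence gives 1.7%, 2.5% and 5.0%.

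**Two worked cases** (p-values in the printed order):

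| p-values | Literal list | Gated sequence | Holm |
|---|---|---|---|
| 0.30, 0.40, 0.20, 0.04 | claims endpoint 4 | none | none (smallest, 0.04, exceeds 0.0125) |
| 0.014, 0.001, 0.001, 0.001 | claims endpoints 2 to 4 | none (0.014 exceeds 0.0125) | all four (0.014 ranks last and is below 0.05) |

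The literal list can therefore add a claim that Holm rejects, or lose one that Holm allows.

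**How often the readings differ.** The plan's primary assumption is "we expect an effect size of 3% with the standard deviation of the change in liver fat of 2.45". With 68 evaluable patients, taken as 34 per arm (the allocation ratio is not stated), z = 3/(2.45 × √(2/34)) = 5.05, a power of 0.999. The documents give no power for the key secondaries, so the rows below are scenarios. Power is per endpoint at two-sided 0.05. Each range covers ρ from 0.9 to 0.5, by simulation.

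| Scenario | Three readings not all in agreement |
|---|---|
| Every endpoint at z 5.05 | 0.7–1.1% |
| Responder endpoint at z 4.0, others at 5.05 | 5–6% |
| Responder endpoint at z 3.5, others at 5.05 | 13–14% |
| 95% power | 13–23% |
| 90% power | 20–35% |
| 80% power | 27–49% |
| 50% power | 30–53% |
| All nulls true | 5–8% |

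For the literal list against Holm alone, the rates are 0.6–0.8% at z 5.05, 23.5–27.1% at 80% power and 4.5–5.1% when all nulls are true.

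**The case against.** The best defence is that ranking and stopping are part of Holm's definition, so naming the procedure brings them in. On that view the list is a clumsy display of the step levels, error is at most 5%, and the text is ambiguous rather than contradictory. Four free-standing levels summing to 0.104 would also defeat the stated aim of controlling for multiple testing. This has force, and it is reading 1 above. It does not rescue the sentence: the list is offered as the specification of the procedure, and under reading 1 none of its endpoint labels has any business being there. Nothing in the documents says that the name overrides the list.

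Other points stand as limits on size:

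- Error inflation arises only under the literal reading, and its amount depends on assumed correlations.
- The three-way disagreement rates are raised by the gated reading, for which the plan states no gate. Literal list against Holm is the narrower contrast.
- The literal list is not always the more liberal rule. At 80% power and ρ 0.5 it makes a claim that Holm does not in 11% of trials, and the reverse happens in 16%.
- If aspirin works as the plan assumes, the practical effect is small.
- A choice of reading after the results is a possibility that the wording leaves open; nothing shows that it was intended.

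**Conclusion.** The concern holds. The plan names one procedure and prints another, and no other part of the document reconciles them. This should be fixed.

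Under the literal reading, familywise error within the key secondary family is about 5.4% to 7.6% over the plausible correlation range, with an upper bound of 10.4%. Under ranked Holm or a gated sequence it is at most 5%. Literal and Holm conclusions differ in under 1% of trials at the plan's primary effect size and in about a quarter at 80% power per endpoint. The correlations, the key secondary power and equal allocation are assumptions, since the documents supply none of them. Only the key secondary claims are at stake.

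**What to change.** Replace the endpoint-specific list with wording such as: the four key secondary p-values will be ordered from smallest to largest and compared with 0.0125, 0.0167, 0.025 and 0.05 in turn; testing stops at the first non-significant result. Record the change, with its date, before database lock and unblinding.

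If the printed endpoint order is what is wanted, call it a fixed-sequence test, at 0.05 per step with a stop at the first failure. That replaces the printed levels and is a change of design, so it should be described as one.

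The same sentence should say whether the family is tested only if the primary endpoint is significant. The plan is silent on this, and the 5% control above covers the key secondary family alone.

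The cost is a sentence or two of SAP text, with no effect on the sample size or the primary test. The one loss is that the relative MRI-PDFF change no longer has a guaranteed threshold of 0.05.

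### The key secondary endpoints have their own 5% error allowance with no condition on the primary result, and the Holm levels are tied to named endpoints instead of ordered p-values

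*Combined protocol and SAP*

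**What the plan says.** Section II names one primary endpoint: "Primary Efficacy Endpoint: 6-month absolute difference in % hepatic fat fraction (HFF), measured by 1H-MRS". It lists four key secondaries: relative HFF change by MRS, a responder proportion by MRS, and absolute and relative change by MRI-PDFF.

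Section VI.C, under Sample Size, Statistical Power & Multiplicity Testing, attaches a level to the power statement for the treatment difference: "the probability is >90% that the study will detect a treatment difference at a two-sided 0.05 significance level". The same paragraph then says "The Holm procedure to control for multiple testing will be applied to the 4 key secondary outcomes" and gives the levels by endpoint: "P=0.0125 for relative change in HFF by MRS, P=0.0167 for proportion achieving" the responder threshold, followed by 0.025 for absolute PDFF change and 0.05 for relative PDFF change. The remaining secondary and the exploratory outcomes are left unadjusted.

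No section places the primary in the Holm family, divides alpha between the primary and the key secondaries, or makes key secondary testing conditional on the primary. The change list at the end of the document reports no SAP changes after trial initiation, so no such rule was added later.

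**The concern.** There are two gaps in the same paragraph.

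The first is the missing link. The primary uses 0.05 and the key secondaries use a further 0.05. All four key secondaries measure liver fat again, two from the same spectroscopy data as the primary and two from MRI-PDFF in the same scanning session. Suppose the primary gives p = 0.07 and relative MRS change gives p = 0.01. The plan would then allow a formal, multiplicity-adjusted positive statement about liver fat beside a failed primary about liver fat. The plan controls error among the key secondaries but does not say what that control means once the primary has missed.

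The second is how the levels are assigned. Holm gives 0.0125 to the smallest of the four p-values, 0.0167 to the next, and so on, whichever endpoints they belong to. The plan gives each level to a named endpoint. An analyst who follows the printed list as four fixed cut-offs is not running Holm, and the family's 5% control is lost.

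**Working it through.** **Inputs.** From section VI.C: primary level 0.05 two-sided; Holm levels 0.0125, 0.0167, 0.025 and 0.05; effect 3; SD of change 2.45; 68 evaluable participants. Assumed, because the documents do not give them: 1:1 allocation (34 per arm) and a common correlation ρ between the test statistics.

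**The plan's own figures reproduce.**
- Holm levels: 0.05/4 = 0.0125, 0.05/3 = 0.0167, 0.05/2 = 0.025, 0.05/1 = 0.05.
- Effective sample: 80 × 0.85 = 68.
- Power: standard error = 2.45 × √(2/34) = 0.594; 3/0.594 = 5.05; power ≈ Φ(5.05 − 1.96) = Φ(3.09) ≈ 99.9%, which meets the stated figure of more than 90%.

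**Bound across the five tests with true Holm.** The primary contributes at most 0.05 and the Holm family at most 0.05. The total is at most 0.10 under any correlation and any pattern of true nulls.

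**No effect on anything, independent tests.** Holm rejects something only if the smallest of the four p-values is at most 0.0125. The chance of any false claim is therefore 1 − 0.95 × 0.9875⁴ = 1 − 0.95 × 0.9509 = 0.0966.

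**No effect on anything, correlated tests.** Write each statistic as Zᵢ = √ρ·X + √(1−ρ)·Eᵢ, with X and Eᵢ independent standard normal. Then

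P(no rejection) = ∫ ∏ᵢ [Φ((cᵢ − √ρ·x)/√(1−ρ)) − Φ((−cᵢ − √ρ·x)/√(1−ρ))] φ(x) dx,

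with c = 1.960 for the primary and c = 2.498 (level 0.0125) for each key secondary. The third column uses the four printed levels as fixed cut-offs, without the primary.

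| ρ (assumed) | Any false claim, primary + true Holm | Of which: key secondary claimed, primary missed | Key secondary family alone, printed levels as fixed cut-offs |
|---|---|---|---|
| 0 | 9.7% | 4.7% | 10.1% |
| 0.5 | 8.3% | 3.3% | 8.8% |
| 0.7 | 7.1% | 2.1% | 7.6% |
| 0.8 | 6.3% | 1.3% | 6.8% |
| 0.9 | 5.5% | 0.5% | 5.9% |
| 0.95 | 5.1% | 0.1% | 5.4% |

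The second column is the first minus 5%. For the third column at ρ = 0: 1 − 0.9875 × 0.9833 × 0.975 × 0.95 = 0.1006. The sum of the four levels, 0.1042, is the upper bound.

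**A less favourable pattern.** Suppose the primary and one key secondary have no effect while the other three are clearly rejected. The last Holm step is then at 0.05, and the chance of a false claim is 1 − 0.95² = 9.75% at ρ = 0, 7.8% at 0.8 and 7.0% at 0.9. This is a limiting case, and not a likely one when all five endpoints measure liver fat.

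**With a gate on the primary.** If the primary null is true, any false claim first requires a false rejection of the primary, so the rate is at most 5%. If the primary null is false, only the Holm family can produce a false claim, again at most 5%. The primary is still tested at 0.05, so its power stays at about 99.9% on the plan's inputs.

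**The case against.** The strongest reply is that the plan breaks no promise. It names one primary endpoint and applies Holm to the key secondaries only. Nowhere does it claim 5% control over both. Separate control of the primary and of a secondary family is a legitimate choice in an early-phase trial of 80 people. That stands: a reader might infer that the plan violates its own error control, and the documents do not support this.

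A reader might also infer that the plan allows a failed primary to be counted as trial success through a key secondary. No section says so. The text only leaves the status of such a result undefined.

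On size, it is tempting to quote 9.7%. That figure needs independent tests, while the reason for concern is that the endpoints overlap. The correlations are probably high, so under no effect at all the excess is probably 0.5 to 1.3 percentage points. It is also tempting to quote the rate for the primary plus fixed cut-offs, 1 − 0.95 × 0.8994 = 14.6% if independent. That mixes the missing link with the level-assignment problem and sets aside the fact that the plan names Holm.

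A third reading is possible: stepping through the four endpoints in the printed order and stopping at the first failure. That keeps the family within 5%. Under no effect, the rate across primary and key secondaries is then only 6.2% at independence and 5.2% at correlation 0.9. The text does not say that this is what is meant.

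Finally, if the plan's effect and SD hold, the primary almost never misses and a gate would hardly ever bind. That is true, but the rule matters in the case where those assumptions fail.

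**Conclusion.** The point holds as a minor one. The absence of any link is plain from the text. The size of the excess depends on a correlation that the documents do not report, and a single common correlation is itself a simplification, since one key secondary is a responder proportion. Under no effect at all, 0.8 to 0.9 seems plausible for measures this close; 0.7 would give 7.1%.

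The assignment of levels is a separate defect of wording and arguably the more practical one. If the printed cut-offs are applied literally, the family does not have the 5% control that naming Holm implies, whatever happens to the primary.

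**What to change.** The Data Analysis Plan says the SAP is to be finalised before database lock, which gives the occasion to replace the list of endpoint-specific levels with text such as:

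> The four key secondary endpoints will be tested by the Holm procedure on their ordered p-values at an overall two-sided 0.05, for formal claims only if the primary endpoint is significant at two-sided 0.05. Otherwise they will be reported descriptively with confidence intervals.

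This needs no patients and no extra data. The price is that a real key secondary effect cannot be formally claimed if the primary misses. If the sponsor does not want that restriction, the SAP should instead state that key secondary results fall outside any trial-wide 5% error rate. It should still say that the Holm levels follow the ordered p-values.
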